Specific Aim: To determine the dose-effect curves for positive subjective effects (drug liking and good drug effects) and alleviation of smoking urges, as a function of nicotine delivery rate in menthol and non-menthol cigarette preferring smokers.

Hypothesis #1A: Positive subjective effects of nicotine will gradually decline with slower delivery rates, with minimal effects of nicotine delivery rate on urges to smoke.

Hypothesis #1B: Non-menthol smokers, compared to menthol smokers, will have greater responses to nicotine for these outcomes as reflected by a leftward shift in dose-effect curves.

Exploratory Aim #1: To explore the dose-effect curves of nicotine delivery rate for a) reinforcement (assessed with the monetary value of the dose from the Multiple-Choice Procedure (6), b) heart rate and blood pressure, and c) tobacco withdrawal severity (assessed with self-report symptoms and cognitive performance).

Exploratory Aim#2: To examine the impact of plasma nicotine levels and rate of nicotine metabolism (measured by plasma hydroxycotinine/cotinine ratio) on the dose-effect curves for the main study outcomes.

Exploratory Aim#3: To examine sex differences for the main study outcomes.

5. Background:

Nicotine control policies to reduce the addictive potential of tobacco products:

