We have developed IV nicotine infusion protocols to answer key questions regarding the addictive properties of nicotine and individual differences in tobacco smoking behavior that are mediated by nicotine (12, 18-21). Subjects in **Fig 1** were 187 adult male and female dependent smokers that had abstained from smoking for ~10 h (adapted from Jensen KP et al. 2015)(19). The average age was 36 years (SD = 8.9). Subjects received infusions of saline and doses of nicotine at 0.12 and 0.24 mcg/kg/second for 60s (0.5 and 1 mg nicotine per 70 kg body weight doses) in uniform order. The doses of nicotine delivered in this session approximate the total dose of nicotine delivered by smoking 0.5 and 1.0 tobacco cigarettes. **Fig 1** shows the subjective ratings of pleasurable and aversive effects after IV saline and nicotine infusion (19). IV nicotine increased ratings of pleasurable effects (main effect for dose: $F_{(2,3025)} = 124.7$, $P < 0.01$), while it had a more subtle effect on ratings of aversive effects (main effect for dose: $F_{(2,3025)} = 1.85$, $P = 0.16$). **Fig 1c** shows that nicotine withdrawal symptoms (M-NWS total score), the urge to smoke for reward (BQSU factor 1), and the urge to smoke to reduce negative symptoms (BQSU factor 2) were lower at the end of the IV nicotine infusion session relative to overnight-abstinence baseline (main effect of time for MNWS: $F_{(1,188)} = 64.85$, $P < 0.01$; BQSU Factor 1: $F_{(1,184)} = 116.6$, $P < 0.01$; BQSU Factor 2: $F_{(1,184)} = 66.6$, $P < 0.01$). Withdrawal symptoms were assessed by the Minnesota Nicotine Withdrawal Scale (M-NWS) and Brief Questionnaire on Smoking Urges.

[figure not shown]

Fig 1. IV nicotine infusion to study the addictive properties of nicotine. IV nicotine induces (A) positive and (B) negative subjective effects and (c) suppresses nicotine withdrawal symptoms. $n=187$, dependent smokers, ** $p < 0.01$, * $p = 0.16$. (Jensen et al. *Neuropsychopharmacology*, 2015)

Summary of preliminary studies:

- We have developed IV nicotine infusion protocols to answer key questions regarding the addictive properties of nicotine and individual differences in tobacco smoking behavior that are mediated by nicotine (12, 18-20, 22).
- IV nicotine doses infused at 0.12 and 0.24 mcg/kg/second for 60s (~0.5 and 1 mg doses) induce pleasurable (“drug liking”, “feels good”) drug effects, aversive drug effects and suppresses withdrawal symptoms (**Fig 1**), similar to smoking.

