infusion of nicotine. The most rapid nicotine infusion rate, 0.24 mcg/kg/s, has proven to be well tolerated in our prior studies (12, 18-20, 22). The total weight-adjusted nicotine dose will not exceed 1.2 mg. Subjects will complete baseline assessments after an indwelling catheter is inserted into an antecubital vein for safety and drug administration. Immediately prior to the start of the infusion (@ min 0) and at intervals following the start of the infusion, heart rate, blood pressure, DEQ and withdrawal assessments will be taken as shown in **Fig 2**. At the end of the session (min 120), subjects will complete the Drug versus Money Multiple-Choice Form (\$MCP) (23).

Session procedures: Before the experimental session, subjects will be required to abstain from smoking for 10h, which will be verified by expired air CO levels \leq 10 ppm (33, 34). Subjects will also be asked to refrain from consuming alcoholic beverages and drugs prior study participation, which will be verified by urine drug screening and breathalyzer before the sessions. Subjects that are non-compliant will be rescheduled or, if they are repeatedly non-compliant, discharged from the study. Subjects will be instructed to drink their typical amount of caffeinated beverages to minimize caffeine withdrawal, which could confound the study measures. Subjects will be instructed not to eat for 4 h before the sessions to minimize heartburn or nausea that can be associated with IV nicotine administration. A light meal will be provided at the end of each session.

Fig # 2 Schedule of Events: Experimental Session*

| Time point | Measures and Events |
|------------|--|
| Baseline | CO, urine and blood samples, HR/BP, M-NWSC, BQSU, SAFTEE, CPT |
| 0 min | IV Infusion starts |
| 1 min | HR/BP, DEQ, plasma nicotine |
| 3 min | HR/BP, DEQ, plasma nicotine |
| 5 min | HR/BP, DEQ, plasma nicotine |
| 8 min | HR/BP, DEQ, plasma nicotine |
| 10 min | IV Infusion ends, plasma nicotine |
| 11 min | HR/BP, DEQ, BQSU, plasma nicotine |
| 12 min | HR/BP, plasma nicotine |
| 13 min | HR/BP, DEQ, plasma nicotine |
| 15 | HR/BP, DEQ, plasma nicotine |
| 18 | HR/BP, DEQ, plasma nicotine |
| 20 | HR/BP, DEQ, plasma nicotine |
| 25 | HR/BP, DEQ, |
| 30 min | HR/BP, DEQ, BQSU, CPT, M-NWSC |
| 40 | HR/BP, DEQ, plasma nicotine |
| 50 | HR/BP, DEQ, plasma nicotine |
| 60 | HR/BP, DEQ, BQSU, M-NWSC CPT, plasma nicotine |
| 90 | HR/BP, DEQ, BQSU, M-NWSC CPT, plasma nicotine |

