Positive subjective effects of nicotine will be assessed with the “Like the Drug Effects” and “Good Drug Effects” items from the DEQ, consistent with the FDA Guidance on abuse potential assessment (10). These items have been shown to correlate with the abuse potential of drugs of abuse. Effects will be tested using linear mixed effects models with peak change on each DEQ item as a response variable, cigarette-preference (menthol vs. non-menthol) as a between-subject factor, nicotine delivery condition as a within-subject factor and their interaction. Period effects will be controlled for by including test day as an additional predictor in the models. Random effects for subject and condition within subject will be used to account for correlations between repeated measures. Because of the potential skewed distributions of the subjective effects data, transformations will be applied as necessary. We will evaluate the main and interactive effects of menthol cigarette preference and delivery rate. We anticipate statistically significant main effects of menthol-preference, nicotine delivery rate and a significant interaction between menthol-preference and nicotine delivery rate. To better understand the dose effects of nicotine delivery rate and whether they are moderated by menthol preference, we will construct specific contrasts among the four doses to test whether there is an indication of significant linear, quadratic, linear on log-scale or sigmoidal dose-response relationships across, or within menthol-preference groups. The possible dose-response curves identified by the specific mean contrasts will be compared by fitting linear and non-linear (as necessary) dose-response models with continuous dose and selecting the best-fitting model by the Akaike’s Information Criterion (AIC).

To test for an effect of delivery rate on smoking urges, assessed by the BQSU (Factor 1 and 2) scores, we will use similar modeling approach described for subjective effects but we will also include time as a within-subject factor with outcomes for minute 0, 10, 30, 60 and 120. We anticipate a significant main effect of menthol-preference, nicotine delivery rate and potentially a significant interaction between menthol-preference and nicotine delivery rate.

Rationale for sample size:

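### The smoking-urge model counts the pre-infusion score as one of five outcome times, so its delivery-rate and menthol-by-rate effects are 0.8 of the post-infusion effect

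*Combined protocol and SAP*

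**What the plan says.** Section 10 models the DEQ items first, "with peak change on each DEQ item as a response variable". The predictors are menthol preference, delivery condition, their interaction and test day. On the correlation structure it says: "Random effects for subject and condition within subject will be used to account for correlations between repeated measures". On the tests it says: "We will evaluate the main and interactive effects of menthol cigarette preference and delivery rate".

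The BQSU Factor 1 and Factor 2 scores get a similar model, to which "we will also include time as a within-subject factor with outcomes for minute 0, 10, 30, 60 and 120". For these scores the plan states: "We anticipate a significant main effect of menthol-preference, nicotine delivery rate and potentially a significant interaction between menthol-preference and nicotine delivery rate". It gives no baseline BQSU covariate and no change score, and it neither names nor rules out an interaction with time.

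Section 9.A times the minute-0 assessments "Immediately prior to the start of the infusion (@ min 0"). Fig 2 schedules the BQSU at Baseline and at 11, 30, 60, 90 and 120 minutes. The model therefore lists a minute 10 that is not scheduled for the BQSU and leaves out the scheduled 90 minutes.

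Hypothesis 1A (section 4) expects positive subjective effects to decline with slower delivery, "with minimal effects of nicotine delivery rate on urges to smoke".

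**The concern.** A score taken before any nicotine cannot carry an effect of delivery rate. Counting it as an outcome and averaging over time pulls the rate main effect and the menthol-by-rate interaction toward zero.

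The Specific Aim asks for the dose-effect curve for alleviation of urges, so the height of that curve is itself a result. The direction matters too. Hypothesis 1A sets a rate effect on liking against little or none on urges. Liking is tested on peak change, which is not averaged with a pre-infusion time; urges are tested on an average that includes one. The dilution favours the predicted contrast, and the plan gives no margin for what would count as a minimal effect.

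The lack of baseline adjustment has a second consequence. Menthol preference is not randomised, so a menthol main effect on raw urge scores can reflect a craving difference that existed before the infusion. The menthol-by-rate interaction does not have this problem.

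**Working it through.** **The plan's own figures.** A two-sample noncentral t with d = 0.8, two-sided alpha 0.025 and 31 per group gives 80.0% power, as stated for menthol. A noncentral F with f = 0.5, N = 56, 3 and 52 df and noncentrality f²N = 0.25 × 56 = 14 gives 79.6%, close to the stated 80% for rate with 28 per group. Both reproduce.

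**Dilution.** The stated random effects make the five times within a session exchangeable, so with complete data they carry equal weight. Conditions are randomised to sessions, so the expected rate effect at minute 0 is zero. With post-infusion effects p1 to p4:

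(0 + p1 + p2 + p3 + p4)/5 ÷ (p1 + p2 + p3 + p4)/4 = 4/5 = 0.80

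- The time profile does not matter. Flat (1, 1, 1, 1), decaying (1, 0.8, 0.5, 0.2) and early-only (1, 0.3, 0, 0) profiles all give 0.80.
- Simulated raw scores (60 replicates) gave 0.7995 for rate and 0.782 for menthol-by-rate; the latter departs through chance baseline differences.
- Reading the response as change from minute 0 does not help. That change is zero at minute 0 by construction, and both ratios were exactly 0.800.
- Keeping minute 0 and adding 90 minutes would give 5/6 = 0.83.

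**Illustrative power.** The documents give no BQSU variances, so these inputs are assumptions.

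- Effect: in section 5, urges "were lower at the end of the IV nicotine infusion session relative to overnight-abstinence baseline", with F(1,184) = 116.6 and 66.6 for Factors 1 and 2. In SDs of change these are √(116.6/185) = 0.79 and √(66.6/185) = 0.60. Half of each, 0.397 and 0.300, is taken as the fast-slow difference.
- Variance: total 1 = subject s + condition-within-subject c + residual e. The within-session correlation s + c is 0.5, so the SD of change is √(2 × 0.5) = 1. The cross-session correlation s is 0, 0.2 or 0.4.
- Variance of a two-session difference: 2(c + e/5) for the planned five times (effect × 0.8) and for the five Fig 2 post-infusion times; 2(c + e/5 − c²/(c + e)) with baseline adjustment.
- Test: noncentral t, N − 1 df, two-sided alpha 0.025.

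Example (Factor 1, N = 70, s = 0): the planned variance is 2(0.5 + 0.1) = 1.2, the noncentrality 0.8 × 0.397/√(1.2/70) = 2.43, and power 56%. Adjusted, the variance is 2(0.6 − 0.25) = 0.7, the noncentrality 0.397/√(0.7/70) = 3.97, and power 95%.

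Power (%) at s = 0 / 0.2 / 0.4:

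| | Planned | Five post-infusion times | Same, baseline-adjusted |
|---|---|---|---|
| N=70, Factor 1 | 56 / 75 / 97 | 77 / 92 / 100 | 95 / 98 / 100 |
| N=70, Factor 2 | 33 / 49 / 81 | 50 / 70 / 95 | 76 / 84 / 97 |
| N=56, Factor 1 | 45 / 64 / 92 | 66 / 84 / 99 | 89 / 94 / 99 |
| N=56, Factor 2 | 26 / 39 / 70 | 41 / 58 / 89 | 65 / 74 / 92 |

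A simulation of all five sessions with pooled error (0.40 SD, N = 70, 4,000 replicates) agreed: planned 58/77/98%, post-infusion 80/93/100%, adjusted 96/98/100%, with a planned-to-post estimate ratio of 0.801 to 0.802. Over within-session correlations of 0.2 to 0.8 and cross-session shares of 0 to 95%, the planned test never beat the adjusted one.

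**If rate-by-time is tested instead**, with minute 0 kept as an ordinary outcome and a constant post-infusion effect (N = 70): a 1-df post-minus-baseline contrast has variance 2 × 1.25e and 75% (Factor 1) or 49% (Factor 2) power at every s. The 12-df omnibus test over four rates and five times has 38% or 19%.

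**The case against.** The strongest reply is that the plan is incomplete rather than wrong. The DEQ model it copies includes its factors' interaction, so adding time could be read as adding rate-by-time, with minute 0 as the reference for alleviation. What the plan anticipates is not an exclusive list of tests. This stands in part: a rate-by-time test is not diluted, and the plan does not exclude one. But the effects it names for urges are the diluted ones, and the undiluted reading would have to be written in.

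The power figures are also open to challenge, fairly:

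- The pilot change is an uncontrolled before-after change over a session with saline and two nicotine doses. It is not a rate contrast, and halving it is a choice.
- A linear contrast over four equally spaced rates does slightly better as planned: 61/80/98% against 56/75/97% (Factor 1, N = 70).
- The comparators add the 90-minute score. With only the four listed post-infusion times, the unadjusted figures are 75/90/99.6%, and the adjusted ones fall by 0 to 4 points.
- The plan's own effect size for rate is f > 0.5. With four equally spaced rates this is a fast-slow gap of 0.5/0.373 = 1.34 SD, where the planned test keeps over 99.9% power (N = 56, same correlations). Yet on the F formula that reproduces the plan's 28 per group, f falling from 0.5 to 0.4 with an unchanged SD takes power from 79.6% to 55.9%. The power loss depends on the model and is not established.

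Finally, section 10 anticipates a significant rate effect on urges, and dilution works against that expectation. That is true, and it shows that sections 4 and 10 disagree about which result is predicted. None of these points changes the factor of 4/5.

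**Conclusion.** The concern holds. For the effects the plan names, the rate and menthol-by-rate estimates for urges are 0.80 of the mean post-infusion effect. This is exact given complete data and the stated random effects; missing times or another covariance structure would shift it slightly. It does not apply to a rate-by-time test or, in the same way, to the menthol main effect.

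The power cost is only illustrative. Under the assumptions above (0.40 SD, N = 70), a real effect would be missed in 44/25/3% of trials as planned, against 5/2/<1% with baseline adjustment. At 0.8 SD (N = 56) the planned test still has about 98% power or more. The main harm is a urge curve that is 20% too low, in the direction that favours Hypothesis 1A. It can be removed without cost.

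**What to change.** - Model the post-infusion BQSU scores at the Fig 2 times (11, 30, 60, 90 and 120 minutes). Use that session's pre-infusion score as a covariate and add the subject's mean baseline, so that the slope is within-subject. Keeping baseline as an outcome with a common minute-0 mean across conditions is an acceptable equivalent.
- Name rate and rate-by-time as the tests for urges.
- For Hypothesis 1B on urges, rely on the planned menthol-by-rate interaction, including nicotine versus saline, and not on the menthol main effect on raw scores.
- Reconcile Hypothesis 1A (little rate effect on urges) with section 10 (a significant one), and state which result would support 1A.

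The cost is a change of analysis wording. The Baseline and 90-minute BQSU scores are already in Fig 2, so no visit, sample or measurement is added.

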Justification to include smokeless tobacco and e-cigarette users: We will include users of smokeless tobacco or e-cigarettes given the high prevalence of e-cigarette and smokeless tobacco products among young adults (26-28). As noted above, urine cotinine will be used to biochemically confirm the subjects' nicotine consumption and smoking status and used as a covariate in all analyses if required.

Subject sampling to account for sex, race, dependence symptoms, and smoking frequency: We are planning to enroll Caucasian and African-American smokers while maintaining an approximately equal male-to-female ratio.

We will create dichotomous variables to be used as a covariate to match groups on race (European American and African American) and sex because of the potential influence of race and sex on smoking behavior and nicotine pharmacokinetics (22, 29). We will also control for differences in the frequency of smoking because it may influence the behavioral effects nicotine (30-32); a continuous variable based on the reported smoking frequency (cigs per day) will be used as a covariate in the analyses if required.

8: Recruitment:

Hundred subjects will be recruited. The goal is to have 70 completers, 35 menthol and 35 non-menthol cigarette smokers.

9. Research Plan:

A. Overview

Experimental Summary: Subjects will complete five separate experimental sessions on five separate days with each session beginning around 8 AM (Fig 2). Each session (1 to 15 days apart) will include one infusion condition that will be either saline or nicotine at four different infusion rates. The five infusion conditions will be assigned randomly to one of the five experimental sessions. All infusions will last 10 minutes and be controlled by two infusion pumps, a saline infusion pump and a nicotine infusion pump. The 0.24 mcg/kg/s condition will include a 1 minute infusion of nicotine followed by a 9 min infusion of saline; the 0.096 mcg/kg/s condition will include a 2.5 minute infusion followed by a 7.5 min infusion of saline; the 0.048 mcg/kg/s condition will include a 5 min infusion of nicotine followed by a 5 min infusion of saline; the 0.024 mcg/kg/s condition will include a 10 min infusion of nicotine and no infusion of saline; and the placebo condition will include a 10 min infusion of saline and no

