Nicotine administration: Nicotine 1mg/mL solution for injection obtained from US Specialty Formulations LLC, Bethlehem, Pennsylvania will be prepared for IV infusion by the research pharmacy at the West Haven VA. Nicotine and saline will be administered by infusion pump via a single IV catheter located in a forearm vein. We have followed these procedures in our previous studies, which were completed without any adverse effects attributed to nicotine or other safety concerns. Each session will include one 10-minute infusion that will be controlled by a combination of two infusion pumps. One infusion pump will control nicotine delivery and one infusion pump will control saline delivery. The infusions pumps will be operated silently and be toggled on and off to reach the 10-min total infusion time for the given condition. Subjects will be blinded to the infusion pump procedures. For this project, an amendment to [name] IND for IV nicotine will be submitted.

Justification for the nicotine dose and nicotine delivery rate: For this proposal, we selected one active dose of nicotine, 1.0 mg per 70 kg body weight, and placebo (saline). The 1.0 mg per 70 kg body weight nicotine dose approximates the total nicotine dose delivered to a smoker when they smoke a typical tobacco cigarette (53). Our previous studies of ND smokers indicates that 1.0 mg per 70 kg body weight dose delivered in 1 min (0.24 mcg/kg/s) induces robust drug liking subjective effects and suppresses withdrawal symptoms. However, this dose deliver rate is faster than what a smoker might encounter while smoking a cigarette. The moderate delivery rates, 0.096 and 0.048 mcg /kg/s, that approximates the rates of intake encountered while a smoker smokes a typical cigarette over 5 min. The slowest nicotine delivery rate, 0.024 mcg/kg/s, was chosen to approximate the nicotine intake rate that an individual might encounter from a newer E-cig device (2,5). The total weight-adjusted nicotine dose will not exceed 1.2 mg.

10. Data analysis methods

Hypothesis #1: To determine the dose-effect curves for positive subjective effects (drug liking and good drug effects) and alleviation of smoking urges, as a function of nicotine delivery rate in menthol and non-menthol cigarette preferring smokers.

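### No smoking-urge score is taken while the four delivery rates differ in nicotine delivered, so a minimal rate effect on urges can be concluded only from minute 10/11 onward and cannot be set against the peak-liking result

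*Combined protocol and SAP*

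**What the plan says.** Section 9.A defines the conditions by how long nicotine runs within a fixed 10-minute infusion. At the extremes, "The 0.24 mcg/kg/s condition will include a 1 minute infusion of nicotine followed by a 9 min infusion of saline" and "the 0.024 mcg/kg/s condition will include a 10 min infusion of nicotine and no infusion of saline". The intermediate rates, 0.096 and 0.048 mcg/kg/s, run for 2.5 and 5 minutes. Section 9.D sets one active dose for all of them, 1.0 mg per 70 kg.

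For urges, section 10 takes the liking model and adds time: "we will also include time as a within-subject factor with outcomes for minute 0, 10, 30, 60 and 120". In Fig 2 the first BQSU after baseline is in the minute-11 row ("HR/BP, DEQ, BQSU, plasma nicotine"), followed by minutes 30, 60, 90 and 120.

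The two positive subjective effects, liking and good effects, come from the DEQ. Section 9.C.2 (item 3.2) and Fig 2 list somewhat different DEQ times, but both start at minute 1 and run to minute 120. Section 10 analyses peak change.

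Hypothesis 1A in section 4 predicts that positive effects decline at slower rates, "with minimal effects of nicotine delivery rate on urges to smoke". Section 10, by contrast, expects a significant main effect of delivery rate on urges. Section 9.C.2 gives a reason for the DEQ times; no section gives one for the BQSU times.

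**The concern.** Hypothesis 1A is a statement about two outcomes together: liking depends on rate, and urge relief hardly does. Section 6 uses the same idea to argue that a slow product might relieve urges with low addiction liability. If liking is sampled while the rates are at work and urges only once every condition has received its full dose, a rate effect on liking alone could reflect when each was measured. Faster onset of relief at faster rates would go unrecorded. The first urge score also compares conditions at different times since nicotine stopped, so a rate effect found there has more than one explanation.

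**Working it through.** **Inputs.** Rates and nicotine durations: section 9.A. Total dose: section 9.D. Urge times: section 10 and Fig 2. DEQ times: section 9.C.2 item 3.2 and Fig 2.

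**1. Reproduce the stated dose.** Dose = rate x 60 x nicotine minutes:
- 0.24 x 60 x 1 = 14.4 mcg/kg
- 0.096 x 60 x 2.5 = 14.4 mcg/kg
- 0.048 x 60 x 5 = 14.4 mcg/kg
- 0.024 x 60 x 10 = 14.4 mcg/kg

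14.4 x 70 = 1,008 mcg, or 1.008 mg per 70 kg, which agrees with the stated 1.0 mg.

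**2. Nicotine delivered by minute t** = rate x 60 x min(t, nicotine minutes), in mcg/kg:

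| Minute | 0.24 | 0.096 | 0.048 | 0.024 |
|---|---|---|---|---|
| 1 | 14.4 | 5.76 | 2.88 | 1.44 |
| 3 | 14.4 | 14.4 | 8.64 | 4.32 |
| 5 | 14.4 | 14.4 | 14.4 | 7.2 |
| 8 | 14.4 | 14.4 | 14.4 | 11.52 |
| 10 and later | 14.4 | 14.4 | 14.4 | 14.4 |

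The amounts differ only strictly between minutes 0 and 10.

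**3. Ratings inside that window.** BQSU: none under section 10, none under Fig 2. DEQ: four under Fig 2 (1, 3, 5, 8) and five under item 3.2 (1, 2, 4, 6, 8). Nothing else fills the gap. The withdrawal checklist first recurs at minute 30. Item 3.2 speaks of 12 DEQ items but names nine, and none of the nine is urge to smoke.

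**4. Minutes since nicotine ended at the first urge score**, fastest to slowest:
- minute 10: 9, 7.5, 5 and 0
- minute 11: 10, 8.5, 6 and 1

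**5. Plasma levels (illustration only).** The documents give no kinetic parameters, so these are assumed. For zero-order input over D minutes and two-phase decline, the level at t is proportional to the sum over phases of w/(kD) x [exp(-k(t - T)) - exp(-kt)], with T = min(t, D) and k = ln 2 / half-life. Assumed: slow-phase weight 0.2-0.4, fast half-life 3-8 min, terminal half-life 60-180 min. Ratio of the fastest to the slowest condition:

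| Minute | Fastest : slowest |
|---|---|
| 1 | 10 |
| 3 | 2.8-3.2 |
| 5 | 1.4-1.8 |
| 10-11 | 0.54-0.82 |
| 30 | 0.84-0.98 |
| 60 | 0.93-0.98 |

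With wider assumptions (slow-phase weight 0.1-1.0, fast half-life 3-15 min, slow 60-120 min) the ratio is 0.43-0.97 at minutes 10-11 and 0.78-0.97 at 30. The reversal holds throughout both ranges; its size depends on the assumptions.

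**The case against.** The strongest reply is that scoring urges after full delivery is a control. The design fixes total dose so that only rate varies, and a score at minute 10 or later compares rates at matched dose. A score at minute 1 would compare a full dose with a tenth of one. This stands: the BQSU times answer a legitimate question, and an urge test confined to the infusion would have the opposite fault. But it is a different question from the one the DEQ peak answers, because that peak can fall inside or after the infusion.

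It is also fair that section 6 asks whether a slow product can relieve urges enough to help smokers quit, and says nothing about onset within ten minutes. The BQSU from minute 10/11 to 120 bears directly on that.

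A reader might go further and infer that the schedule largely builds in the null that Hypothesis 1A predicts. The documents do not support that. Under the assumed kinetics the first urge score may fall where levels still differ, with the slowest condition higher. An earlier, higher peak could also leave relief that later scores detect. Section 10 itself expects a significant rate effect and describes no formal test of a dissociation. How much any null would owe to timing cannot be calculated from the documents, and the step from plasma level to urge is itself assumed.

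**Conclusion.** The point holds in a limited form. It is exact, and needs no assumption, that the rates differ in delivered nicotine only between minutes 0 and 10, that no BQSU score lies there under either schedule, and that liking is sampled there and summarised by its peak. So the plan cannot detect a rate effect on urges during the infusion. A minimal rate effect can be concluded only from minute 10/11 onward, and it is not comparable with the DEQ peak result. Any claimed dissociation is confounded with sampling time. Only the size of the concentration difference at minutes 10-11 rests on assumed kinetics. Urges are part of the Specific Aim, so this limits what the trial can conclude; the liking analysis is unaffected.

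**What to change.** Preferred: add one 100-mm urge-to-smoke item to the DEQ at its existing times, including the pre-infusion rating in item 3.2. Analyse its peak change (largest fall) with the mixed model used for the other DEQ items. Label it secondary, so that section 10's alpha split for two outcome measures is unchanged. Present the in-infusion time course descriptively only, because rate is mixed there with dose received so far. Keep the BQSU for relief at matched total dose. The cost is a few seconds per assessment, one extra model, and reliance on a single item beside a validated scale.

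If the item is not added: restate the urge half of Hypothesis 1A as relief from minute 10/11 onward, after the full dose, and do not claim a dissociation from the DEQ peak. This costs only wording.

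In either case:
- Reconcile minute 10 in section 10 with minute 11 in Fig 2.
- Include the minute-90 BQSU, which Fig 2 collects and section 10 leaves out of the model.
- Reconcile the minimal rate effect in Hypothesis 1A with the significant one expected in section 10.
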